6.5.3 Previous and concomitant medication

Previous medication is defined as a medication with at least one dose taken before the date of first dose of study drug.

Concomitant medication is defined as a medication with at least one dose taken between the date of first dose (inclusive) and end of safety emergent period.

Previous and concomitant drug use will be recorded, including non-prescription medication, complementary and alternative medications. Handling of missing date information for prior or concomitant medications is given in Section [7.11.2](#)

If the medication start date and end date are both missing, the medication will be counted as previous and concomitant.

If the medication start date is missing and the end date is prior the date of first drug administration, the medication will be counted as previous medication.

If the medication start date is missing and the end date is after the date of first drug administration, the medication will be counted as previous and concomitant medication.

Renal transplant status (Yes or No), and the date of renal transplant (if applicable) will be derived. Similarly, ESA use after study treatment (Yes or No), and the start date of ESA use after study treatment (if applicable) will be derived.

6.5.4 Variables related to study drugs

Randomization/Treatment Arms

[Table 11](#) below presents the groups to which subjects are randomized.

Table 11 Treatment arms

Randomization Arm Code (ARMCD)	Randomization Arm (ARM)
A	Roxadustat - TIW
B	ESA (Darbepoetin Alfa or Epoetin Alfa)

Analysis date of First Dose Intake

Date of first study drug dose intake is collected in the Day 1 visit in the Randomization eCRF. In case of a missing/partial date, the earliest available date will be used. It will be on the same day than the randomization date and before the next dose date.

Analysis Date of Last Dose

Date of Last Study Drug Dose is collected at the End of Treatment visit in the End of Treatment eCRF. When this date is not known, all efforts should be made to obtain the date from the investigator. If it is still missing after all efforts have been made, then the visit date of the End of Treatment Visit will be used as the Analysis Date of Last Dose. If subject is lost to follow-up and none of these dates are available, then the date of the last available assessment during the study will be used.

Duration of exposure in days

For each subject, the Length of Time on treatment will be calculated in days, using the following formula:

(‘Analysis Date of Last Dose’ - ‘Analysis Date first dose intake’) + 1

Amount of Prescribed (planned) Medication

Roxadustat

The number of milligrams prescribed at each visit (including unscheduled visits) is captured in the *Changes in Dosing* eCRF. The investigator reported dose and frequency will be used when available. For first administration, the IRS reported dose and frequency will be used.

The prescribed weekly dose at each visit (including unscheduled visits) will be calculated as prescribed dose x 3 as the prescribed frequency is TIW for roxadustat.

Each visit will have an associated start and end date as follows:

- Each visit (including unscheduled) will have an associated start date,
- Each visit (including unscheduled) will have an associated end date. This date will be the date of the next consecutive visit [including unscheduled visits and EOT] minus 1 day.

Time periods of interest are defined below (monthly is defined as a period of 4 weeks or 28 days) as follows:

Time Period	Analysis Start Day	Analysis End Day*
Week 4 (Month 1)	Day 1	Day 28
Week 8 (Month 2)	Day 29	Day 56
Week 12 (Month 3)	Day 57	Day 84
Week 16 (Month 4)	Day 85	Day 112
Week 20 (Month 5)	Day 113	Day 140
Etc....		
Week 104 (Month 26)	Day 701	Day 728
Treatment Period	Day 1	Day of EOT
Day 1 - Week 28	Day 1	End Day of Month 7 (day 196)
Day 1 – Week 36	Day 1	End Day of Month 9 (day 252)

*or EOT whichever is first

This will allow us to calculate the amount of prescribed medication in a time period as the sum of the daily prescribed amount within the time windows defined above.

In addition, amount of prescribed medication in mg/kg will be calculated. To convert a dose given in mg into a dose in mg/kg, the body weight recorded at day 1 will be used.

Darbepoetin alfa and epoetin alfa

The same methodology will be used for darbepoetin alfa and epoetin alfa. Note that prescribed frequency for darbepoetin alfa is once weekly, once every other week, or once every four weeks, and the prescribed frequency for epoetin alfa is: once weekly, twice weekly, three times weekly, or once every other week. The unit for darbepoetin alfa is microgram (μg), the unit for epoetin alfa is IU.

In addition, amount of prescribed medication in $\mu\text{g}/\text{kg}$ and IU/kg will be calculated. To convert a dose given in μg into a dose in $\mu\text{g}/\text{kg}$ or in IU into a dose in IU/kg, the body weight recorded at day 1 will be used.

Amount of Consumed Medication

Roxadustat

The consumed Investigational Product Medication is captured in the *Study Drug Roxadustat Accountability* eCRF which includes the following kit information:

- Kit strength, kit treatment, kit dispensed, date of kit dispensed, kit strength total number of tablets dispensed
- Kit returned, returned date, total number of tablets returned

For each kit, the following will be calculated:

- Start Day of Exposure for each kit: study day kit dispensed
- End Day of Exposure for each kit: study day kit returned – 1 Day
- Amount dispensed for each kit: kit strength x number of tablets dispensed
- Amount returned for each kit: kit strength x number of tablets returned

- Amount consumed for each kit: amount dispensed – amount returned
- Daily consumed dose for each kit: amount consumed/(end day of exposure-start day of exposure +1)

The same methodology as described for Amount Prescribed (planned) Medication will apply to calculate amount of consumed medication for each time period by summing up the different daily consumed amount of the different kits on a given day (subjects will be dispensed more than one kit on a given visit).

In addition, amount of consumed medication in mg/kg will be calculated.

Darbepoetin alfa and epoetin alfa

The same methodology will be used for darbepoetin alfa and epoetin alfa. Note that instead of tablets dispensed/returned, there will be syringes dispensed/administered. Administration date is not captured, therefore the start and end day of exposure will be defined as follows:

- Start Day of Exposure for each kit: study day kit dispensed
- End Day of Exposure for each kit: for kits administered, the next consecutive date that the ESA was dispensed – 1 Day

In addition, amount of consumed medication in µg/kg (darbepoetin alfa) and IU/kg (epoetin alfa) will be calculated.

Compliance

Compliance will be calculated for the time periods defined in Amount of Prescribed (planned) Medication. Compliance in % will be calculated for each time period (not reported cumulatively) as:

$$\frac{\text{Amount consumed during time period}}{\text{Amount prescribed during time period}} \times 100$$

The following compliance categories will be defined:

- less than 50% (significant drug noncompliance)
- at least 50%, less than 75% (moderate drug noncompliance)
- at least 75% (acceptable compliance)
- unknown

Dose Changes for roxadustat, darbepoetin alfa and epoetin alfa

Dosing changes are collected in the Study Drug Roxadustat - Dosing Decisions eCRF for roxadustat, in the Study Drug Darbepoetin - Dosing Decisions eCRF for darbepoetin alfa and in the Study Drug Epoetin alfa- Dosing Decisions eCRF for epoetin alfa.

For example, for roxadustat, a change from 200 TIW to 250 TIW is a change of 600 mg to 750 mg per week.

The same applies for darbepoetin alfa and epoetin alfa, but not weekly as it could be administered weekly, bi-weekly, monthly, or other frequencies.

For each subject the total number of dose changes, dose increases, dose decreases, and dose holds will be calculated.

7 STATISTICAL METHODOLOGY

7.1 General Considerations

- All statistical comparisons will be made using two sided tests at the $\alpha=0.05$ significance level unless specifically stated otherwise. Null hypotheses for superiority testing will be of no treatment difference and corresponding alternative hypothesis will be two-sided. Null hypotheses for non-inferiority testing will be of inferiority of roxadustat treatment and will be one-sided at the $\alpha=0.025$.
- All data processing, summarization, and analyses will be performed using SAS® Version 9.3 (SAS Enterprise Guide 4.3) or higher. Specifications for tables, data listings and figures (TLFs) formats can be found in the TLF Specifications for this study.
- All data will be summarized by treatment arm (roxadustat and ESA), type of ESA treatment (darbepoetin alfa and epoetin alfa) and for the total, unless specified otherwise. For all results split by type of ESA treatment, previous ESA treatment before randomization will be separated in two categories (darbepoetin alfa or epoetin), unless specified otherwise.
- For continuous variables that are recorded as “< X” or “> X”, the value of “X” will be used in the calculation of summary statistics. The original values will be used for the listings.
- All percentages will be rounded to one decimal place and lined up by the decimal place. The percentage will be suppressed when the count is zero.
- For continuous variables, descriptive statistics will include the number of subjects (n), mean, standard deviation, median, minimum and maximum. Frequencies and percentages will be displayed for categorical data. Percentages by categories will be based on the number of subjects with no missing data, i.e. will add up to 100%. Number of missing values will be shown in the frequency tables
- All data included in summary tables, inferential analyses or figures will also be listed.
- Listings will be done on all randomized subjects and all assessments (all collected data in the eCRF will be listed except the physical examination data).
- Pre-dialysis vital signs including blood pressure measurement will be used for analysis, unless otherwise specified.
- For the SAF population analyses, the actual treatment will be used. For all other analysis populations, the planned treatment will be used.

For the definition of subgroups of interest please refer to Section [7.8](#).

7.2 Study Population

For this section, unless specified otherwise, PPS refers to the analysis set which excludes from the FAS all the subjects violating criteria at subject level from [Table 4](#) See Section [5.3](#) and Classification specifications for more details.

7.2.1 Disposition of Subjects

The following subject data will be summarized and presented:

- Number and percentage of subjects with informed consent, who discontinued before randomization and randomized (overall only),
- Number and percentage of subjects randomized in each analysis set, by treatment arm, type of ESA treatment and overall,
- Number and percentage of subjects who completed and discontinued treatment, by primary reason for treatment discontinuation, by treatment arm and type of ESA treatment for randomized subjects, SAF, FAS and PPS;
- Number and percentage of subjects who completed and discontinued the study, by primary reason for study discontinuation, by treatment arm and type of ESA treatment, for randomized subjects, SAF, FAS and PPS;
- Number and percentage of subjects who completed the post study safety follow-up period, for all subjects who prematurely discontinued the study;
- Number and percentage of subjects for post study follow-up status, for all randomized subjects within 2 years; and
- Number and percentage of subjects excluded from PPS by reason for exclusion defined in Section [5.3](#) by treatment arm and type of ESA treatment, for the FAS.

The following data will be presented graphically by treatment arm and type of ESA treatment for the SAF and PPS:

- Treatment discontinuation by reason using bar chart;
- Treatment discontinuation by time interval and reason using bar chart; and
- Time to treatment discontinuation using a Kaplan-Meier plot.

In addition, the following graphs will be done to explore missing patterns and support efficacy analyses, by treatment arm, for the All Randomized and PPS:

- Treatment discontinuation for lack of efficacy, using a cumulative incidence plot;
- Treatment discontinuation for adverse event, using a cumulative incidence plot;
- Treatment discontinuation for withdrawal by subject, using a cumulative incidence plot.

Time intervals will be analyzed using the following categories:

- Less than 2 weeks
- At least 2 weeks, less than 4 weeks
- At least 4 weeks, less than 12 weeks
- At least 12 weeks, less than 24 weeks
- At least 24 weeks, less than 36 weeks
- At least 36 weeks, less than 52 weeks
- At least 52 weeks, less than 78 weeks
- At least 78 weeks, less than 104 weeks
- 104 weeks or more
- Unknown.

In addition, the randomization stratification strata from both sources (CRF and IRS) will be reported by treatment arm. Discrepancy between stratification from CRF and IRS will be summarized and the total number of patients with discrepancy overall and for each stratification factor will be provided.

Subjects who had a screen failure will be listed.

All other available data will also be listed.

All data collected during the Post-Study Follow up period will be listed by visit (i.e., type of contact, subject status and occurrence of overnight hospitalizations).

7.2.2 Protocol Deviations

Protocol deviations, as defined in the study protocol (Section 8.1.6: Protocol Deviations) will be assessed for all randomized subjects. The number and percentage of subjects meeting any criteria will be summarized for each criterion and overall, by treatment arm, type of ESA treatment and overall, as well as by study site. Subjects deviating from a criterion more than once will be counted once for the corresponding criterion. Subjects who have more than one protocol deviation will be counted once in the overall summary. A data listing will be provided by site and subject.

The protocol deviation criteria will be uniquely identified in the summary table and listing. The unique identifiers will be as follows:

- PD1 - Entered into the study even though they did not satisfy entry criteria,
- PD2 - Developed withdrawal criteria during the study and was not withdrawn,
 - PD2_1 Withdrawal of consent
 - PD2_2 Pregnancy
 - PD2_3 Significant non compliance
 - PD2_4 ESA rescue therapy (roxadustat subjects)
 - PD2_5 Organ transplant
- PD3 – Received wrong treatment or incorrect dose
 - PD3_1- Received wrong treatment kit
 - PD3_2- Received incorrect dose
 - PD3_3- Study drug non compliance
- PD4 – Received excluded concomitant treatment
 - PD4_1- Received prohibited medication
 - PD4_2- Received restricted medication

7.2.3 Demographic and Other Baseline Characteristics

Demographic and other baseline/screening characteristics will be summarized by descriptive statistics and frequency tabulations.

Number and percentage of subjects randomized in each country and site will be presented for the SAF, FAS, All Randomized and PPS.

Descriptive statistics for age, weight, body mass index (BMI) and height at screening will be presented. Frequency tabulations for sex and race will be presented. Descriptive statistics and frequency tabulations will also be presented for the subgroup variables presented in Section 7.8. Additionally, demographic and other baseline characteristics will be presented for the following variables:

- Average screening Hb value as continuous and categorical (≤ 11.0 g/dL versus >11.0 g/dL),
- Baseline Hb as continuous,
- Iron repletion at baseline, as a categorical value (see Section 6.5.2).

Demographic and baseline characteristics summaries above will be done for the All Randomized, SAF, FAS and PPS. This table will be repeated for subjects randomized after amendment 2.0 (or any further amendment) is implemented.

Selected demographics collected at screening will be done on Screen Failure subjects.

All Medical History will be analyzed using the SAF, as described below:

Medical History including anemia, chronic kidney disease (CKD), cardiovascular disease and targeted medical history are coded in MedDRA, they will be summarized by System Organ Class (SOC) and Preferred Term (PT).

Anemia history, CKD history, targeted medical history (diabetes type I and II, hypertension and dyslipidemia), cardiovascular disease history, tobacco history and family history of cardiovascular disease will be summarized.

The number and proportion of subjects with each typical symptom for CKD will be described, as well as the number and proportion of subjects with each typical symptom for anemia.

Demographic and baseline data will also be listed.

7.2.4 Previous and Concomitant Medications

Previous and concomitant medications are coded with WHO-DD, and will be summarized by therapeutic subgroup (ATC 2nd level), chemical subgroup (ATC 4th level) and preferred WHO name for the SAF.

Subjects taking the same medication multiple times will be counted once per medication.

Treatment history for anemia will be summarized separately.

Missing dates' imputation rules are detailed in Section 7.11.2

7.3 Study Drugs

Roxadustat (=Investigational Product Medicine) is for oral administration and supplied as red coated oval tablets of 20, 50 and 100 mg.

Darbepoetin alfa (=Comparative Medicine) is administered by SC or IV injection, and supplied as a solution for injection in a pre-filled syringe of 10, 20, 30, 40, 60 and 100 μ g.

Epoetin alfa (=Comparative Medicine) is administered by SC or IV injection, and supplied as a solution for injection in a pre-filled syringe of 1000, 2000, 3000, 4000, 6000 and 8000 IU.

7.3.1 Exposure

The following information on drug exposure will be presented by treatment arm and type of ESA treatment, for the SAF.

Exposure related variables are defined in Section [6.5.4](#)

Descriptive statistics will be produced for:

- The average weekly dose (roxadustat, darbepoetin alfa and epoetin alfa) the subject was exposed to during the treatment period (in mg, µg or IU and in mg/kg, µg/kg or IU/kg), by month, during the first 28, 36, and 52 weeks; and overall.
- Number and percentage of subjects with dose changes, dose increases, dose decreases or dose hold.
- Number of times for dose changes, dose increases, decreases or dose hold.

Duration of exposure will be summarized in two ways:

- Descriptive statistics and frequency tabulations will be presented;
- Exposure time will be categorized according to the following categories:
 - Less than 2 weeks
 - At least 2 weeks, less than 4 weeks
 - At least 4 weeks, less than 12 weeks
 - At least 12 weeks, less than 24 weeks
 - At least 24 weeks, less than 36 weeks
 - At least 36 weeks, less than 52 weeks
 - At least 52 weeks, less than 78 weeks
 - At least 78 weeks, less than 104 weeks
 - 104 weeks or more
 - Unknown.

Counts and percentages of subjects in each of these categories will be summarized.

For roxadustat, box-plots of average weekly dose and average weekly dose/kg by month will be produced. Separate box-plots for darbepoetin alfa will be produced, using a different unit (µg instead of mg), and separate box-plots will be produced for epoetin alfa too, using IU instead of mg. In the box-plots, the prescribed amount will be used.

Study drug medication will also be listed showing for each subject and each visit the dispensed kit numbers and the actual medication in each kit. For instance, if a subject randomized to ESA, at one visit was mistakenly dispensed a kit containing roxadustat then the listing will show that roxadustat was given to the subject on the intended visit.

7.3.2 Treatment Compliance

Overall compliance with the dosing schedule will be examined for subjects in the SAF whose total study drug count and first and last days of treatment are known.

Percent overall compliance will be summarized in two ways, during the first 28 weeks, 36 weeks, 52 weeks and overall:

- Descriptive statistics will be presented,
- Percent compliance categories will be categorized according to the categories defined in Section [6.5.4](#)

Counts and percentages of subjects in each of these categories will be summarized.

Results will be displayed by treatment arm and type of ESA treatment.

7.4 Analysis of Efficacy

For all continuous efficacy variables, in addition to inferential analyses, descriptive statistics will be produced for the actual values and for the changes from baseline (BL) by visit.

Similarly, for all categorical efficacy variables, frequencies and proportions will be produced by analysis visit.

Quantitative endpoints with repeated measures over time will be analyzed using MMRM and ANCOVA with MI, as the preferred methods for imputation of missing data.

For this section, unless specified otherwise, PPS refers to the analysis set which excludes from the FAS all the subjects violating criteria at subject level from [Table 4](#). See Section [5.3](#) and Classification specifications for more details.

Unless otherwise specified, the efficacy analyses will be performed for All subjects, and by Type of ESA treatment (Darbepoetin Subjects and Epoetin Subjects).

For efficacy analyses by treatment arm (Roxadustat versus ESA), the covariates list will include the variable Previous ESA treatment (epoetin versus darbepoetin alfa). But for efficacy analyses by Type of ESA treatment (Subgroup Darbepoetin and Subgroup Epoetin), because the Type of ESA treatment is based on the Previous ESA treatment, then this variable Previous ESA treatment will not be included in the covariates list.

For the efficacy analyses by subgroup, the subgroup analysis by Previous ESA treatment will not be presented in tables, as this analysis is already performed by Type of ESA treatment (Subgroup Darbepoetin and Subgroup Epoetin).

Analysis visits windows are detailed in Section [7.11.4](#).

Missing data imputation rules are detailed in Section [7.11.1](#)

7.4.1 Analysis of Primary Endpoint(s)

There are two separate regionally based primary efficacy endpoints in this study, depending upon whether the data are being filed to support submission to the US FDA or to Ex-US health authorities, such as the European Medicines Agency (EMA).

7.4.1.1 EU (EMA) Primary Endpoint

7.4.1.1.1 Primary Analysis of the EU (EMA) Primary Endpoint

The primary EU (EMA) efficacy endpoint will be analyzed using the PPS.

The change from baseline to the average Hb of weeks 28 to 36, without having received rescue therapy within 6 weeks prior to and during this 8-week period, will be computed from the Mixed Model of Repeated Measures method (MMRM), adjusting for stratification factors (covariates defined below), comparing roxadustat to ESA (pooled darbepoetin alfa and epoetin alfa). After fitting the data, a computation statement will be added to the model to calculate the average Hb values estimate during the period under consideration.

Difference of least square means (roxadustat minus ESA) and its 2-sided $100*(1-\alpha*2)\%$ confidence interval will be estimated for the change from baseline to the average of weeks 28 to 36. The significance level α is fixed by the parametric chain procedure explained below.

The primary analysis of the EU (EMA) primary efficacy endpoint will be tested both in the overall population and in the subset of patients defined as subjects with an average prescribed weekly epoetin or darbepoetin dose within the last four weeks prior to randomization ≤ 200 IU/kg or ≤ 1 μ g/kg respectively, following a parametric chain procedure.

The two null hypotheses to be tested are:

- H_{A0} : Hb change from baseline to the average of weeks 28 to 36 in the roxadustat arm \leq Hb change from baseline to the average of weeks 28 to 36 in the ESA arm minus 0.75 g/dL in the total study population
- H_{B0} : Hb change from baseline to the average of weeks 28 to 36 in the roxadustat arm \leq Hb change from baseline to the average of weeks 28 to 36 in the ESA arm minus 0.75 g/dL in the subset population

The alternative hypotheses H_{A1} and H_{B1} are defined as the negation of the null hypotheses H_{A0} and H_{B0} respectively. The information fraction (subjects in the subset population/total study population) will be calculated at the time of database hardlock.

The overall one-sided significance level (alpha) is fixed at 0.025. The overall alpha will be equally allocated to each of the two null hypotheses defined above. In case of an information fraction of 0.80, this rule will lead to a significance level of 0.0174.

The following table ([Table 12](#)) lists a selection of one-sided significance levels (alpha) to be considered should the IF varies from the protocol.

Table 12 Information Fraction (IF) and One Sided Significance Level (alpha) for the Primary Endpoint

Information Fraction (IF)	alpha (1-sided)
0.5	0.0147
0.6	0.0154
0.7	0.0162
0.8	0.0174
0.9	0.0191
0.97	0.0216

Following the parametric chain procedure, if at least one of the two null hypotheses is rejected at the significance level of 0.0174, the other one can be tested at a significance level of 0.025 while still controlling the overall type I error. The study will be successful for the EU primary efficacy endpoint if either of the null hypotheses is rejected, i.e., if the lower limit of the two-sided $100*(1-\alpha*2)\%$ CI for the difference in least square means from the MMRM model is greater than -0.75g/dL.

If both null hypotheses are rejected, secondary endpoints will be assessed on the overall population. Otherwise, secondary endpoints will not be formally tested.

The covariates will be:

- Previous ESA treatment (epoetin versus darbepoetin alfa);
- Region (region A versus region B);
- History of cardiovascular, cerebrovascular or thromboembolic diseases (Yes versus No)[#];
- Average prescribed weekly ESA dose prior to randomization (≤ 200 IU/kg epoetin or ≤ 1 μ g/kg darbepoetin alfa versus > 200 IU/kg epoetin or > 1 μ g/kg darbepoetin alfa)^{*};
- Baseline Hb value (Continuous).

[#]: This covariate is derived according to a list of cardiovascular disease preferred terms received from the study physician after softlock.

^{*}: For the analyses, the average prescribed weekly ESA dose prior to randomization will be taken from the screening procedure form, in the eCRF. Upon review of data, this covariate was excluded from analysis as number of subjects in the high dose group was too low for the variable to be meaningful.

For these covariates, the IRS value used at randomization will be compared to the eCRF value.

In case of stratification errors during the randomization process, the analysis will use the correct covariates as recorded on the eCRF for the subject.

MMRM model:

An MMRM model will be run for the purpose of implicit imputation of missing data by using all the available information from the observed data via the within-patient correlation

structure. The analysis will be based on the estimated difference between the two treatment arms overall mean effects throughout the evaluation period (weeks 28 to 36) based on this MMRM model.

The model will contain treatment arm, region, CV History, previous ESA treatment, visits and visit by treatment as categorical variables. It will also contain baseline Hb and baseline Hb by visit as continuous variable.

The unstructured covariance pattern model will be used. If the algorithm for unstructured covariance pattern does not converge, then heterogeneous Toeplitz structure will be used. If this later model does not converge either, then the (homogeneous) Toeplitz structure will be tried. Finally, if none of them converge, first order autoregressive (AR (1)) as a covariance structure will be used to achieve convergence.

A similar model as the general example below will be used:

$$c_{ikjn} = \text{intercept} + \beta_n M_{\text{baseline},ikjn} + \tau_i + \alpha_n + (\alpha\tau)_{in} + \gamma_k + \varepsilon_{ikjn}$$

where

- c_{ikjn} is each analysis visit change from baseline of subject j in treatment arm i , and stratum k at time n ,
- β_n is the slope of c_{ikjn} at visit n as a function of the baseline Hb,
- $M_{\text{baseline},ikjn}$ is the baseline measurement of subject j in treatment arm i and stratum k at time n ,
- τ_i , is the mean effect of treatment arm i ,
- α_n is the mean effect at time n ,
- $(\alpha\tau)_{in}$ is the interaction term between treatment arm i and time n ,
- γ_k is the mean effect of stratum k ,
- ε_{ikjn} is the residual at time n for subject j in treatment arm i and stratum k .

The SAS procedure will be similar to the following:

```
proc mixed;
  class subject_id treatment previous_ESA_treatment region cv_history
    visit;
  model change = treatment previous_ESA_treatment region cv_history
    baseline_Hb visit treatment*visit;
  repeated visit /subject = subject id type=un;
  lsmeans visit*treatment / cl alpha = 0.05;
  estimate 'Roxadustat v.s. ESA averaged at weeks 28-36'
    treatment 1 -1
    treatment*visit 0 0 0 0 .. 0.2 0.2 0.2 0.2 0.2 -0.2 -0.2 -0.2
    -0.2 / cl;
  where visit in ('Week1', 'Week2', ..., 'Week8', 'Week10', ..., 'Week36');
run;
```

One analysis Hb value for each visit will be used, as defined in analysis windows in Section [7.11.4](#) and [Table 32](#)

Subjects receiving rescue therapy treatment within 6 weeks prior to and during this 8-week period will be set to missing and imputed similarly in the model (see Section [7.11.1](#) for imputation details).

In addition, MMRM least square means and 2-sided 95% confidence intervals will be calculated for each visit for the difference in treatment arms. The results will be presented as least square means and 95% confidence intervals for treatment differences, and also present the nominal p-values for non-inferiority and superiority. MMRM least square means and their 95% confidence intervals will be plotted versus time.

Model checking:

Residual plots will be produced showing the following:

- Model residuals in the y-axis and model predictions in the x-axis,
- Model residuals in the y-axis and baseline Hb in the x-axis.

Different dot styles will be used for the two treatment arms. Solid black symbols will be used for roxadustat and non-solid red symbols will be used for ESA.

Residual plots will be done for the MMRM analysis. The plot will be repeated by visit at Weeks 28, 30, 32, 34 and 36.

In addition, an empirical cumulative distribution function of the residuals will be plotted for the MMRM analysis.

Descriptive analyses

In addition to the inferential analysis, central laboratory and HemoCue hemoglobin Hb values and their associated change from baseline, will be reported descriptively by visit. For central lab Hb values, the average of weeks 28-36 will also be reported.

The following data will be presented graphically, by treatment arm:

- Hb results using mean values (+/- 95% CI) plot
- Hb change from baseline results using mean values (+/- 95% CI) plot.

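### SAP Table 12 pairs an information fraction of 0.97 with a one-sided level of 0.0216, but the rule behind its other five rows gives 0.02145; any excess over 0.025 is small and depends on the realised fraction

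*SAP*

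**What the plan says.** SAP section 7.4.1.1.1 sets up two non-inferiority hypotheses for the EU primary endpoint, one in the total study population and one in the subset on lower prior ESA doses. On error control it states: "The overall one-sided significance level (alpha) is fixed at 0.025". On the split: "The overall alpha will be equally allocated to each of the two null hypotheses defined above". The level depends on the information fraction (IF): "The information fraction (subjects in the subset population/total study population) will be calculated at the time of database hardlock". The worked case reads: "In case of an information fraction of 0.80, this rule will lead to a significance level of 0.0174".

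Table 12, titled "Information Fraction (IF) and One Sided Significance Level (alpha) for the Primary Endpoint", covers other fractions. The SAP says that it "lists a selection of one-sided significance levels (alpha) to be considered should the IF varies from the protocol". Its rows are 0.5, 0.6, 0.7, 0.8, 0.9 and 0.97, and the last is paired with 0.0216. The paragraph after the table describes the first step using 0.0174 only, allows the remaining hypothesis to be tested at 0.025 once one has been rejected, and claims control of the overall type I error. It also states: "The study will be successful for the EU primary efficacy endpoint if either of the null hypotheses is rejected". A footnote to the covariate list drops prior ESA dose from the model because the "number of subjects in the high dose group was too low for the variable to be meaningful".

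**The concern.** The table supplies decision thresholds for a confirmatory primary test. Success needs only one of two rejections, so the common level must be the one at which the chance of at least one false rejection is 0.025. If a row is too high for its stated fraction, the claim of type I error control fails for a plan that applies the row as printed. The error would favour the sponsor and is easy for a regulator to find. The 0.97 row deserves a check because it is the only one off the 0.1 grid, and the footnote on the small high-dose group suggests that the realised fraction may be well above the planned 0.80.

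**Working it through.** **Inputs (SAP 7.4.1.1.1).** Overall one-sided alpha 0.025; equal levels for the two hypotheses; IF = subset size / total size; success on either rejection.

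**Assumption.** The correlation of the two test statistics is √IF. This holds for a nested subset with the same variance and allocation ratio as its complement. The SAP does not state it, so it is tested below against the SAP's own figures.

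**Formula.** With both nulls at the margin, the common level a solves

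1 − Φ₂(c, c; √IF) = 0.025, where c = z(1 − a)

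and Φ₂ is the bivariate normal distribution function. The later retest at 0.025 adds nothing here, because it takes place only after a first rejection.

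**Reproducing the table.** The last column is the family-wise error when the printed level is used at the printed IF.

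| IF | Table 12 | Solved level | Error at printed level |
|---|---|---|---|
| 0.5 | 0.0147 | 0.014693 | 0.02501 |
| 0.6 | 0.0154 | 0.015366 | 0.02505 |
| 0.7 | 0.0162 | 0.016220 | 0.02497 |
| 0.8 | 0.0174 | 0.017370 | 0.02504 |
| 0.9 | 0.0191 | 0.019126 | 0.02497 |
| 0.97 | 0.0216 | 0.021450 | 0.02517 |

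The first five rows match to four decimals, including the 0.0174 given in the text. The sixth does not. Numerical integration and a closed form using Owen's T function agree on these values.

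**Other readings of the rule.** Setting the correlation to IF itself gives 0.0157 at 0.8 and 0.0203 at 0.97. Fixing one hypothesis at 0.0125 and solving for the other gives 0.0213 at 0.8 and 0.0248 at 0.97. Neither matches the rows that are otherwise reproduced. Halving a two-sided 0.05 family gives 0.02145 at 0.97 again.

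**Rounding of the level.** 0.021450 becomes 0.0215 to the nearest fourth decimal, or 0.0214 rounded down, but not 0.0216. Rounding in the sound rows costs at most 0.00005 (IF 0.6). The last row exceeds 0.025 by 0.02517 − 0.02500 = 0.00017, about three times as much.

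**Rounding of the fraction.** Solving backwards, 0.0216 is the exact level for IF = 0.9728 and the nearest four-decimal level for IF from about 0.9719 to 0.9737. All of these print as 0.97. Using 0.0216 across fractions that print as 0.97 gives:

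| True IF | Family-wise error at 0.0216 |
|---|---|
| 0.965 | 0.02546 |
| 0.970 | 0.02517 |
| 0.9728 | 0.02500 |
| 0.9749 | 0.02487 |

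**Candidate levels at IF 0.97.** 0.0214 gives 0.02494, 0.0215 gives 0.02506, and 0.0174 gives 0.0204.

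**Effect on the decision.** The critical value is 2.0218 at 0.0216 and 2.0247 at 0.02145. With the planning figures in SAP section 4 (SD 1.5 g/dL, 300 per arm), the standard error is 1.5 × √(2/300) = 0.1225 g/dL. The confidence limit moves by (2.0247 − 2.0218) × 0.1225 ≈ 0.0004 g/dL, against a margin of 0.75 g/dL.

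**The case against.** The strongest reply is that 0.0216 may be a correct level attached to a rounded fraction. It is right for IF 0.9728, and above that it is conservative. The SAP also calls the table a selection of levels to be considered and puts the calculation of the fraction at hard lock, so the table need not be what fixes the level. The running text names only 0.0174, which at IF 0.97 spends 0.0204. A breach therefore needs three things together: the table value taken literally, a fraction below 0.9728, and both nulls true at the margin. All of this stands, and it limits the consequence. It does not rescue the row, because a reader with a fraction of exactly 0.97 is given the wrong level, and a printed 0.97 cannot show whether 0.025 is respected.

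A reader might infer from the footnote on the small high-dose group that this row is the one that will be applied, and so that the trial exceeds its error rate. The documents do not support that. The footnote is compatible with many fractions, no realised fraction is reported, and for some values that print as 0.97 the level errs on the safe side.

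It is also fair to say that demanding 0.0214 would depart from the table's rounding to nearest, under which the 0.5, 0.6 and 0.8 rows already exceed 0.025 by up to 0.00005.

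**Conclusion.** The 0.97 row of Table 12 is wrong as printed: the rule that yields the other five rows gives 0.02145, and rounding of the level does not explain 0.0216. If the fraction is 0.97 and 0.0216 is applied to both hypotheses, the family-wise one-sided error is 0.02517 instead of 0.025, or 0.7% relative, when both nulls hold at the margin. This is a small defect in a stated primary threshold and is very unlikely to change a conclusion. It does not show that the trial's type I error was exceeded, since that depends on the realised fraction and on which level was used. The text leaves the second point open by naming 0.0174 while the table offers other values. The result rests on the √IF correlation, which the SAP does not state but which the five matching rows support.

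**What to change.** Correct the last row to 0.0215 under the table's own rounding, or to 0.0214 if it is to be rounded down so as not to exceed 0.025. Alternatively, keep 0.0216 and print the fraction with enough decimals to match it (about 0.9728).

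Add one statement to section 7.4.1.1.1. The first-step level is computed at hard lock from the unrounded fraction in the analysed set (the PPS for the primary test), by the bivariate-normal equation with correlation √IF, and is not rounded up. Table 12 is illustration only. Replace the fixed 0.0174 in the paragraph after the table with this computed level. The other rows can then stay rounded to nearest, because none of them sets the threshold.

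The cost is a table cell and a few sentences. The only statistical downside is a marginally stricter threshold if the fraction is 0.97.
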